Recruitment. Recruitment strategies will include local advertising in print media, public service announcements on radio, and referrals to CNRA in the Houston metropolitan area. Additionally, we will utilize the University of Houston SONA system, which provides students credit for participating in various research studies. Access to SONA is made possible with the inclusion of [name] (Consultant). We will also recruit from the Department of Psychiatry Recruitment Registry: HSC-MS-23-0768.

Participants. We will enroll 60 participants to reach a target of **N = 50** completers (25/group). Participants will consist of otherwise healthy treatment-seeking individuals with AUD exhibiting elevated baseline stress/anxiety. All participants will meet the following inclusion and exclusion criteria:

Inclusion criteria. Be treatment-seeking individuals diagnosed with AUD (DSM-5); be at least 18 years old and fluent in English; past month excessive alcohol use (>7 drinks/week for woman, >14 drinks/week for men, >3 drinks/occasion for women>4 drinks/occasion for men)³⁵; exhibit baseline measures of either 1) 8-23 on HAM-A indicative of mild to moderate anxiety, 2) 14-26 on PSS Score indicative of moderate stress, or 3) ≥ 2 on DMQ-R questions related to drinking indicating that individuals drink at least “some of the time” to cope; and exhibit increased stress reactivity (increased physiological response and/or self-report) at the baseline stress reactivity assessment.

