Brief Counseling. At baseline, all participants will receive the NIAAA booklet "Rethinking Drinking: Alcohol and Your Health" providing research-based information related to alcohol use (RethinkingDrinking.niaaa.nih.gov). Study therapists will go over the booklet with the participant at the initial visit and at subsequent weekly visits using motivational interviewing techniques. At each visit, participants will also be assessed for recent alcohol use (self-report, ETG, BrAC), alcohol craving (PACS), and stress/anxiety (HAM-A, PSS). At the end of the study, referrals to local alcohol treatment services will be provided as needed.

Participant Payment & Compensation. Participants will receive \$50 for completing the baseline screening, \$25/visit for attending study visits (9 visits), \$25/assessment for completing stress reactivity

Table 2. Time Course for Assessing Stress-Induced Relapse Risk

Time (pm)	Study Procedures
3:00	Assess Craving, BAAD, Stress, Cortisol, HR, BP
3:15	Cold Pressor Task
3:20	Assess Craving, BAAD, Stress, HR, BP
3:45	Assess Craving, BAAD, Stress, Cortisol, HR, BP

assessments (3 assessments), \$10/week for medication compliance (8 weeks), and \$100 for completing the study (\$530 total). Participants will also receive \$5 compensation for busfare/parking at each study visit.

DATA ANALYTIC STRATEGY

Descriptive Statistics & Confounding Variables Descriptive statistics will evaluate measures of central tendency (continuous) and frequencies (categorical) for study-related variables. General variable relationships will be evaluated using correlation analyses. Preliminary analyses will inspect relationships between sample characteristics (e.g., demographics), predictor variables (e.g., inflammatory markers), and specified outcome variables (e.g., resilience measures) via traditional statistical tests (e.g., chi-square, Mann-Whitney-Wilcoxon, Kruskal-Wallis, and *t*-tests). Sample characteristic variables demonstrating a relationship with both the predictor and outcome variables in a given model will meet criteria as a potential confounder^{104,105} and included as a covariate in such models for hypothesis testing and explored as potential moderators of treatment group effects on experimental outcomes.

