Inferential Paradigm Following recommendations in the literature¹⁰⁶⁻¹⁰⁸, analyses will utilize parallel frequentist and Bayesian statistical inference. Frequentist results yield the probability of the data (or data more extreme), given the null hypothesis, whereas Bayesian results directly yield the probability of an alternative hypothesis¹⁰⁹. If possible, Bayesian analyses will incorporate informative priors as they develop in the literature; otherwise, weakly informative priors will be incorporated as a default. Sensitivity analyses using optimistic and pessimistic, skeptical priors will evaluate prior assumptions¹¹⁰. Assessing the convergence of Bayesian analyses on the posterior distributions via Monte-Carlo Markov chain (MCMC) will use diagnostic evidence including effective sample size and scale reduction factors. Evaluation of posterior distributions will permit statements regarding the probability that effects of varying magnitudes exist, given the data. Statistical analyses will use the most up-to-date stable release version of the R statistical computing environment¹¹¹ using packages rstan¹¹¹ and brms¹¹².

Statistical Modeling Analyses will primarily use generalized linear modeling (GLM). Continuous, count, and dichotomous outcome variables will utilize normal, Poisson/negative binomial, and binomial distribution families respectively, with identity, log, and logit link functions as appropriate. Evaluation of distributional assumptions will use residual plots, formal statistical tests, and posterior predictive checking. Violations of assumptions will be addressed via transformation, robust estimation, stratification, and/or coefficient scaling where appropriate.

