Missingness & Multiple Comparisons Missing data will be addressed via maximum likelihood, explicit modeling of missingness, and/or imputation where appropriate. Each approach is robust to ignorable missingness (i.e. MCAR and MAR). Sensitivity analyses will permit evaluation of the robustness of findings to missing data assumptions. While Bayesian analyses are not influenced by traditional concerns of multiplicity, for the frequentist analyses, all primary outcome variables (those specified by name in the hypothesis statements below) will be evaluated at the $\alpha = 0.05$ statistical significance level. Secondary analyses will examine additional predictor and outcome variables (e.g., other inflammatory markers collected by assays); these and any otherwise *post hoc* analyses will employ false discovery rate (FDR) to control for Type I error.

Specific Analyses

Specific Aim 1: To examine the effects of pioglitazone on stress-induced relapse risk in a laboratory model. **Hypothesis 1a:** Participants receiving pioglitazone will show decreased stress reactivity (heart rate, blood pressure, salivary cortisol) compared to those receiving placebo. **Hypothesis 1b:** Participants receiving pioglitazone will show decreased alcohol craving (subjective, alcohol demand) compared to those receiving placebo.

For hypothesis 1a, GLMM will model each stress reactivity outcomes (primary: heart rate, blood pressure, and salivary cortisol) as a function of the main effects and higher-order interactions between time (baseline to Week 8), treatment (pioglitazone vs. placebo), and CPT measurement point (pre-CPT vs. post-CPT).

Follow-up analyses will examine lower-order interactions longitudinally as well as cross-sectional changes from pre- to post-CPT at each time point. Variable relationships and analyses for hypothesis 1b will follow the patterns stated above for Hypothesis 1a, with craving in place of stress reactivity.

Specific Aim 2: To examine the effects of pioglitazone on drinking, stress/anxiety, and alcohol craving in the natural environment. **Hypothesis 2a:** Participants receiving pioglitazone will show greater reductions in weekly psychometric measures of stress/anxiety measures: PSS and

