HAM-A) compared to those receiving placebo. **Hypothesis 2b:** Participants receiving pioglitazone will show greater reductions in weekly psychometric measures of alcohol craving (primary measures: PACS) compared to those receiving placebo. **Hypothesis 2c:** Participants receiving pioglitazone will show greater reductions in past week alcohol use (primary measures: heavy drinking days as defined by >3 drinks/occasion for women and >4 drinks/occasion for men, average drinks/day) compared to those receiving placebo.

For all hypotheses, GLMM will model primary outcome measures as a function of the main effects and interaction between treatment and time.

Sample Size and Power Considerations

Frequentist Analyses. Power for **Specific Aim 1** is based on the rate at which we may detect the three-way interaction between time, treatment, and CPT measurement point for a given measure of stress reactivity (transformed for normality) across $k = 1000$ Monte Carlo simulations (executed via SAS 9.4). Calculations assume the following conditions: $\alpha = 0.05$, an autocorrelation of $r = 0.50$ between consecutive observations (with a decay of $r = -0.10$ for subsequent observations), and a small correlation of $r = 0.05$ for observations occurring at the same time point across groups. Based on these assumptions, the different sample sizes (pragmatic and pessimistic) stipulated in **Table 3** each provide power to detect small-to-moderate effect sizes (treatment group differences expressed as Cohen's D, with effects unfolding in linear fashion over time). Power for **Specific Aim 2** is based on evaluating reductions in drinks per week. Estimates are derived using G*Power 3.1.9.2. Assuming $\alpha = 0.05$ (two-tailed) and an average baseline of drinks/week across participants (calculated as an average from 14 and 7 drinks/week for a 3:1 ratio of males to females, respectively), the different sample sizes (pragmatic and pessimistic) stipulated in **Table 3** each provide power to detect varying decreases in alcohol consumption.

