Bayesian Analyses. The Bayesian analyses in the current proposal will provide probabilistic estimates of effects for all hypotheses irrespective of statistical power. Moreover, the MCMC approaches utilized in Bayesian analyses do not rely on large sample size assumptions. Bayesian analyses will focus on posterior probabilities ≥ 0.75 (equivalent to a Bayes factor = 0.33 or 3.0) that parameter estimates are greater or less than zero to emphasize the value in discerning model effects.

Table 3. Power estimates for Aims 1 and 2 given different sample and effect sizes.

N (N/group)	SA1: Group Difference (Cohen's D)			SA2: % Decreased Consumption		
	D = 0.50	D = 0.40	D = 0.30	-12.0%	-11.0%	-10.0%
50 (25/25)	100.0%	97.8%	84.6%	97.8%	95.2%	90.8%
40 (20/20)	99.8%	95.0%	71.8%	88.6%	82.5%	74.6%

Cohen's D for observed within-subject effects sizes from our Preliminary Data are as follows: HR (0.8), BP (systolic - 0.5, diastolic - 1.6), cortisol (0.13), PSS (2.1), HAM-A (1.3), BDI (1.2), PACS (1.5), Drinks/week (1.3), Heavy drinking (0.8). Note that Table 3 effect sizes represent between group differences unfolding over time.

STUDY TIMELINE

The time frame illustrated in **Table 4** below is based on conservative estimates. We will continuously monitor our procedures and implement measure to enhance progress as indicated. Our goal is to enroll 60 subjects to achieve 25 completers/group. However, we will continue to enroll subjects based on available resources and subject attrition. Pre-award preparations following pre-award requests (just-in-time (JIT)) will include submitting an initial IRB protocol. Startup will include hiring and training of study staff. Over the course of the study, preliminary and final results will be presented at appropriate scientific conferences (e.g., Research Society on Alcoholism, College on Problems of Drug Dependence, Research Society on Alcoholism, etc.).

Table 4. Study Timeline.

	Year 1													Year 2											
	Month													Month											
	1	2	3	4	5	6	7	8	9	10	11	12	1	2	3	4	5	6	7	8	9	10	11	12	
Pre-award prep																									
	Startup																								
				Phone screens: 250												IRB	NUL	BE	: H	C-N	S-1	-092			
				IRB APPROVAL												DAT	: 10	11/2							

			Intake evaluations: 100											
			Enrollment and randomization: 60 (~3-4 subjects/month)											
			Completion of protocol (~3-4 subjects/month)											

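### The primary models leave the Week 0 arm difference free, which costs precision but causes no bias; a common Week 0 mean recovers it, in Aim 1 only with a suitable covariance

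*Combined protocol and SAP*

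**What the plan says.** For Aim 1, Specific Analyses gives the GLMM terms as "main effects and higher-order interactions between time (baseline to Week 8), treatment (pioglitazone vs. placebo), and CPT measurement point". For Aim 2, "GLMM will model primary outcome measures as a function of the main effects and interaction between treatment and time". In both, baseline is a level of time and treatment has a main effect. The arm difference at Week 0 (and, in Aim 1, the treatment by CPT term at Week 0) is therefore estimated freely.

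No section sets the arms equal at Week 0 or adjusts for the baseline value of the outcome. The covariate rule under Descriptive Statistics & Confounding Variables covers "Sample characteristic variables demonstrating a relationship with both the predictor and outcome variables in a given model" and does not name the baseline outcome. Under Inferential Paradigm, "analyses will utilize parallel frequentist and Bayesian statistical inference", so the same terms serve both sets of models. No random-effects or covariance structure is stated.

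Overall Study Design specifies urn randomisation. The inclusion criteria require that participants "exhibit increased stress reactivity (increased physiological response and/or self-report) at the baseline stress reactivity assessment", which puts the Week 0 stress test before treatment. Table 4 plans "Intake evaluations: 100" and "Enrollment and randomization: 60". The Aim 1 power simulation assumes "an autocorrelation of $r = 0.50$ between consecutive observations (with a decay of $r = -0.10$ for subsequent observations". It does not say whether an observation is a visit or each separate pre- or post-CPT reading.

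**The concern.** With a free Week 0 difference, the treatment by time (by CPT) test subtracts each arm's own baseline mean. In a randomised trial those two means have the same expectation, so the subtraction removes nothing systematic and adds the sampling error of the baseline difference. Setting the Week 0 means equal, or adjusting for the baseline value, subtracts only as much of the baseline as its correlation with the outcome justifies.

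At 25 completers per arm the loss may matter, and Table 1 already schedules the Week 0 measurements that would avoid it. What is at stake is the width of the intervals and the power, not the direction of the estimates.

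**Working it through.** **Set-up.** 25 per arm (Participants), complete data, unit variances, one pre- and one post-CPT value per visit as Specific Analyses models it. The within-visit pre/post correlation is assumed to be 0.5, so the pre-post difference D has variance 2(1 - 0.5) = 1. The percentage cuts in steps 2, 4 and 5 do not depend on that choice. Variance of an arm contrast = 2 x per-person variance / 25.

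**1. The plan's own figure.** Table 3 (Aim 1) could not be reproduced in full, because the scaling of D = 0.50 to 0.30 is not stated. The closest variant (lags through six readings, half-coded effects, contrast variance 0.125) gives 99.9/97.9/85.1% at N = 50 against 100.0/97.8/84.6%. At N = 40 it gives 99.4/94.7/76.5% against 99.8/95.0/71.8%; the last cell misses. The ratios below do not depend on effect size, N or alpha.

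**2. Aim 1, correlations across visits.** Baseline to Week 8 correlation = 0.50 - 0.10 = 0.40.
- Free baseline: 2(1 - 0.40) = 1.20, so 2 x 1.20/25 = 0.096.
- Common baseline: 1 - 0.40² = 0.84, so 2 x 0.84/25 = 0.0672.
- Ratio 0.70, a 30% cut. 1/0.70 = 1.43, equal to 43% more participants. A test with 80% power reaches about 92%.
- With linear time, generalised least squares gives 0.096 against 0.0655, a 32% cut.

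**3. Aim 1, correlations in sequence** (0.5, 0.4, 0.3, 0.2, 0.1 through six readings). The covariance of D at Week 0 and Week 8 is 0.2 - 0.3 - 0.1 + 0.2 = 0.
- Free: 2.00, so 0.160. Common mean for both pre and post values: 0.987, so 0.0789. Cut 51%.
- Linear time: 0.1581 against 0.0619, a 61% cut.

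**4. Entry selection, across-visit reading.** Selecting on baseline reactivity reduces its variance and with it the gain.
- Correlation held at 0.40 and baseline SD k times the Week 8 SD: the free variance is k² + 1 - 0.8k. For k = 0.8 it is 1.00, a 16% cut; for k = 0.6 it is 0.88, a 4.5% cut.
- Regression slope held at 0.40 and baseline variance v: the free variance is 0.84 + 0.36v. For v = 0.5 it is 1.02, an 18% cut.
- Extreme case: all 40 of the 100 intakes not randomised fail on that one outcome. One-sided normal truncation with 60% passing gives v = 0.42 and 0.0794 against 0.0672, a 15% cut. Under the sequence reading, the same case gives 0.1138 against 0.0789, a 31% cut.

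**5. Aim 1 with a person random intercept only.** This model treats D as independent across visits given the person. The constrained estimate then makes no use of baseline reactivity: its per-person variance is 1, so 0.080, whatever the visit correlations. The ratio to the free contrast is 1/[2(1 - rho)], with rho the baseline to Week 8 correlation.

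| Visit correlations | Free | Constrained | Change |
|---|---|---|---|
| 0.5/0.4 | 0.096 | 0.080 | -17% |
| 0.6/0.5 | 0.080 | 0.080 | 0% |
| 0.7/0.6 | 0.064 | 0.080 | +25% |
| 0.8/0.7 | 0.048 | 0.080 | +67% |

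Model-based standard errors are also wrong. At 0.5/0.4 the constrained test has type I error of about 3% (pre/post r = 0.5) or 7% (r = 0.05). It reaches 10% at 0.8/0.7 with r = 0.05. The free test is conservative, at about 2% or less.

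**6. Aim 2, normal outcomes, Week 8.** The plan gives no correlation, so a constant r is assumed. Free 2(1 - r), common 1 - r², cut (1 - r)/2: 35%, 25%, 15% and 10% at r = 0.3, 0.5, 0.7 and 0.8. With linear time: 33%, 19%, 10% and 6%. With the baseline variance halved (assumed): 21%, 14%, 8% and 5%. No figure is offered for count outcomes.

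**7. Simulation.** With the across-visit correlations and the slope estimated at 25 per arm, the cut is about 28%, with type I error 5.0% (free) and 5.1% (adjusted) and no bias. Under the extreme truncation the cuts are 13% (across visits) and 28% (sequence), with type I error 4.8-5.3%.

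**8. Bayesian models.** With weak priors, a 30% variance cut multiplies the posterior SD by √0.70 = 0.84.

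**The case against.** The planned interaction is unbiased and directly tests the greater reductions that Hypotheses 2a to 2c predict. Table 3 claims 84.6% to 100.0% power for Aim 1 at N = 50, so the plan itself shows no shortfall there. The size of the gain rests on correlations the plan states ambiguously (Aim 1) or not at all (Aim 2), and on equal variances that the entry rule may upset. All of that stands, and it makes this an efficiency point with a conditional size. It does not remove the point: the fix keeps the baseline-to-Week 8 contrast, and Table 3 shows only 71.8% at N = 40 and D = 0.30.

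The strongest objection is step 5. A reader might infer that a common Week 0 mean costs nothing and brings 30% everywhere. The documents do not support that. They leave the covariance open, and a random-intercept GLMM would satisfy their wording while turning the constraint into a loss in Aim 1 at high visit correlations.

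A second objection is that equal Week 0 means are guaranteed in expectation only if everyone randomised is analysed. The protocol speaks of completers, but as an enrolment target. It defines no analysis set, and it plans maximum likelihood and/or imputation for missing data. The analysis set therefore has to be stated, but the point survives.

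**Conclusion.** The point holds as a loss of precision. A reader might infer that the treatment by time tests are biased or invalid because of how baseline is handled; they are not, since a free chance difference adds noise and no systematic error.

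With a correctly modelled covariance, the Aim 1 Week 8 contrast would have 30% less variance (correlations across visits, equal variances) or 51% less (lags through all six readings). On the across-visit reading the gain is about 5-18% if entry selection makes the baseline variance clearly smaller. For normal Aim 2 outcomes the gain is (1 - r)/2 at Week 8 with equal variances, and less after selection. For counts the same principle applies approximately on the log scale, without a figure.

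The direction is secure given randomisation, Week 0 values taken before treatment, all randomised participants analysed and an adequate covariance. The size is not secure. The change is worth making before unblinding, as an improvement to a sound test.

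**What to change.** Before unblinding, state in the SAP that all randomised participants are analysed and, for each primary outcome, constrain the arms to a common Week 0 mean. In Aim 1 this applies to both the pre- and post-CPT values; for counts it applies on the log scale. Do so in the frequentist and Bayesian models, and keep the baseline-to-Week 8 contrast as the test.

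For Aim 1, pair the constraint with a covariance that lets the pre-post difference correlate across visits. Examples are an unstructured 6 x 6 matrix, or person random effects for both intercept and CPT point plus visit-level terms. Do not use the constraint with a person random intercept alone.

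Alternatively, adjust the Week 8 pre-post difference for the Week 0 pre-post difference (Aim 1), or the Week 8 value for the Week 0 value (Aim 2). State that the test is then the post-baseline treatment effect. Two traps on this route:
- A person-level baseline mean as the Aim 1 covariate recovers only 17% (0.096 to 0.080).
- Keeping treatment by time after removing Week 0 would test only Week 4 to 8 (Aim 1) or Week 1 to 8 (Aim 2).

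The cost is SAP wording, model code and a few more covariance parameters. Table 1 already schedules the Week 0 values, so no extra visits, participants or measurements are needed.

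### The Specific Aim 1 power in Table 3 does not follow from the stated assumptions: either the power is too high or the effect size D is mislabelled

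*Combined protocol and SAP*

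**What the plan says.** In the combined protocol and SAP, Sample Size and Power Considerations (Frequentist Analyses) bases Aim 1 power on detecting "the three-way interaction between time, treatment, and CPT measurement point for a given measure of stress reactivity", using 1000 simulations at alpha 0.05. It assumes "an autocorrelation of $r = 0.50$ between consecutive observations", falling by 0.10 for later observations, and a correlation of 0.05 "for observations occurring at the same time point across groups". The two sample sizes in Table 3 are said to "each provide power to detect small-to-moderate effect sizes (treatment group differences expressed as" Cohen's D, "with effects unfolding in linear fashion over time". The text under Table 3 repeats the definition: "Note that Table 3 effect sizes represent between group differences unfolding over time".

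The test has three visits (Assessment of Stress Reactivity: baseline, Weeks 4 and 8). Specific Analyses for Hypothesis 1a defines the "CPT measurement point (pre-CPT vs. post-CPT") factor, so there are two points per visit.

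Table 3, Aim 1 columns:

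| Per group | D = 0.50 | D = 0.40 | D = 0.30 |
|---|---|---|---|
| 25 | 100.0% | 97.8% | 84.6% |
| 20 | 99.8% | 95.0% | 71.8% |

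**The concern.** A three-way interaction is a difference of differences compared between arms. It usually has low power in a sample of this size, so 84.6% power for a D of 0.30 with 25 per group needs explaining.

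The text does not allow the table to be checked directly. It does not say which SD scales D, or whether D is a Week 8 difference, a per-visit step or a model coefficient. It does not give the full pre/post-by-visit covariance or the fitted model. Sidedness is given only for Aim 2 ("two-tailed) and an average baseline of drinks/week across participants"). The 0.05 correlation across groups has no obvious meaning, because the groups contain different people.

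Table 3 is the only frequentist power justification for Aim 1, and Missingness & Multiple Comparisons tests each named primary outcome at 0.05. A reader who trusts the table could take a null Aim 1 result as evidence against small-to-moderate effects.

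**Working it through.** **Contrast.** For each participant, take (post − pre at Week 8) − (post − pre at baseline), and assume that all of D falls on it. Order the six observations pre/post within baseline, Week 4 and Week 8. Read the stated decay as lag correlations 0.5, 0.4, 0.3, 0.2, 0.1, with outcome SD 1.

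- Var(post − pre) at each visit: 2(1 − 0.5) = 1.0.
- Covariance of the baseline and Week 8 differences: 0.2 − 0.1 − 0.3 + 0.2 = 0.
- Contrast variance V = 1 + 1 = 2.0. Generalised least squares with linear time gives 1.976.

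**Power.** Two-group noncentral t with df = 2n − 2, alpha 0.05 and noncentrality δ = (mD/√V)·√(n/2). Here m = 1 if D is the Week 8 difference, and m = 2 if D accrues per CPT visit (D at Week 4, 2D at Week 8).

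Example, n = 25 and D = 0.30: 0.30/√2 × √12.5 = 0.75, so power is 11.4%. With m = 2, δ = 1.5 and power is 31.2%. With m = 4, δ = 3.0 and power is 83.6%.

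| Two-sided power (%), D = 0.50 / 0.40 / 0.30 | 25 per group | 20 per group |
|---|---|---|
| Table 3 | 100.0 / 97.8 / 84.6 | 99.8 / 95.0 / 71.8 |
| D at Week 8 (m = 1) | 23.2 / 16.5 / 11.4 | 19.3 / 14.1 / 10.0 |
| D per CPT visit (m = 2) | 68.8 / 50.0 / 31.2 | 58.7 / 41.4 / 25.8 |
| 4D at Week 8 (m = 4) | 99.8 / 97.5 / 83.6 | 99.2 / 93.6 / 74.4 |

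A 10,000-run simulation at 25 per group agrees: 23.4/16.4/11.0, 69.1/49.9/31.0 and 99.8/97.6/83.6% for m = 1, 2 and 4. One-sided testing at 25 per group gives 34.0/25.5/18.3% (m = 1) and 79.4/62.8/43.4% (m = 2). If D is taken directly as the contrast in its own SD, two-sided power at 25 per group is 41/28/18%. Noise from 1000 simulations is too small to explain the gap: at 84.6% the standard error is √(0.846 × 0.154/1000) = 1.1 points.

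**Other covariances, none stated in the plan (25 per group, two-sided).**

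- Visit correlations 0.5/0.4 crossed with pre/post 0.5: V = 2(1 − 0.5) × 2(1 − 0.4)/1 = 1.2. Power is 35.3/24.4/15.8% (m = 1) and 88.5/71.6/47.5% (m = 2).
- Pre/post 0.50, same-condition visits 0.5/0.4, all other pairs 0.05: V = 2.4 − 4(0.50) + 4(0.05) = 0.6. With m = 2, power is 99.4/94.7/76.5%, and 97.8/88.9/66.5% at 20 per group. This matrix is close to singular (smallest eigenvalue 0.015), and every cell is still below Table 3. One-sided, it gives 99.8/97.5/85.4% at 25 per group, near the table, but 77.7% against the stated 71.8% at 20 per group.

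**Back-calculation.** For a single-df two-sided test, power depends only on the contrast divided by its own SD. The 100.0% cell cannot be inverted. The others give:

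| Cell | Contrast, own SD | Multiple of D | Outcome SDs if V = 2.0 | Multiple of D |
|---|---|---|---|---|
| 25, D = 0.40, 97.8% | 1.147 | 2.87 | 1.62 | 4.06 |
| 25, D = 0.30, 84.6% | 0.860 | 2.87 | 1.22 | 4.05 |
| 20, D = 0.50, 99.8% | 1.571 | 3.14 | 2.22 | 4.44 |
| 20, D = 0.40, 95.0% | 1.170 | 2.92 | 1.66 | 4.14 |
| 20, D = 0.30, 71.8% | 0.823 | 2.74 | 1.16 | 3.88 |

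For D = 0.30 to reach 84.6% with 25 per group, V would have to be (0.30/0.860)² = 0.12 with m = 1, or (0.60/0.860)² = 0.49 with m = 2, instead of 2.0.

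**The case against.** The strongest reply is that the simulation may be sound and only its description incomplete. A Week 8 contrast of 4D under the same lag correlations comes within 3 points of every cell, and five of the six cells lie within 95% simulation error for 1000 runs. On that view the fault is an undefined scale for D, and the label small-to-moderate is conventional for D between 0.30 and 0.50. The plan also does not say that the six observations form one chain. That layout gives a pre/post pair within one session the same 0.50 as measurements four weeks apart, and other layouts move per-visit power at D = 0.30 from 31% to 48% or 77%. The main calculation does not use the 0.05 correlation. The back-calculation assumes a single-df two-sided test.

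Much of this stands. The 11% and 31% figures are conditional and are not upper limits, and nothing here shows that the simulation code was wrong. It does not rescue the text. No multiplier of 4 is stated, and with it D = 0.30 would stand for a 1.2 SD interaction. Reading 0.05 as the same-visit pre/post correlation lowers per-visit power at 25 per group to 61/43/27% (other cross pairs 0.05) or 65/46/29% (other cross pairs 0). Treating time as categorical, with a two-df test, also lowers power.

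**Conclusion.** The concern holds. With D read as the plan describes it, no Aim 1 cell of Table 3 is reproduced. At D = 0.30 and 25 per group, the stated 84.6% compares with about 11% (Week 8 difference) or 31% (per-visit step). These figures rest on a six-observation layout with lag correlations 0.5 to 0.1, complete data and a two-sided 0.05 test. Allowing for other covariances, the conclusion is that either the power is overstated or the effect attached to it is about four times the D shown (2.7 to 3.1 times when measured in the contrast's own SD). The statement about small-to-moderate effects is unsupported in both cases.

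This is a fault in the power statement and should be fixed. It is not an argument for more participants: the Innovation section ties the study's size to the funding mechanism, and the Bayesian estimates are to be reported irrespective of power.

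**What to change.** In Sample Size and Power Considerations, state:

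- the scale of D: which SD, and whether it is a Week 8 difference, a per-visit step or a model coefficient (with its coding);
- the sidedness of the Aim 1 test;
- the full 6 × 6 pre/post-by-visit covariance, and what the 0.05 correlation across groups means;
- the model fitted in the simulation.

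Then re-run the simulation, replace the Aim 1 columns of Table 3, and drop the small-to-moderate wording unless the new results support it.

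Also report the effect detectable with 80% two-sided power. In SDs of the three-way contrast this is about 0.81 with 25 per group and 0.91 with 20, for a single-df test. If the lag correlations above are confirmed, these equal 0.809 × √2 = 1.14 and 0.909 × √2 = 1.29 outcome SDs. Otherwise, recompute them from the stated covariance.

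The cost is one simulation run and a text and table correction, with no change to sample size, analyses or procedures. The stated Aim 1 power will probably be less favourable.
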